**COMMON SIDE EFFECTS**

Side effect severity	Investigator response
Noticeable but tolerable	Continue therapy and dose escalation
Bothersome and barely tolerable	Reduce dosage to the last dose tolerated without stopping treatment
Intolerable	Discontinue nortriptyline for one week and then restart it at the lower dosage that was previously tolerated

**Endocrine metabolic:**

Weight gain - Continue study medication with dose escalation as planned.

**Gastrointestinal:**

Constipation - Continue study medication with dose escalation as planned. Recommend patient to add fiber supplement and to increase fluid intake and drink eight ounce glasses of water daily.

Loss of appetite - Continue study medication with dose escalation as planned.

Nausea - Continue study medication with dose escalation as planned.

Bloating - Continue study medication with dose escalation as planned.

Dry Mouth - Continue study medication with dose escalation as planned. Patient can use sugarless hard candy, gum, or ice chips. Saliva substitutes may be needed.

**Neurologic:**

Asthenia - Continue study medication with dose escalation as planned.

Dizziness - Make sure patient is taking entire dose at bedtime. This symptom generally subsides after a few weeks. If continues, reduce dose to prior tolerable dose and maintain this dose for remainder of study. Usually dizziness is due to orthostatic hypotension and can be reduced by having the patient change positions slowly.

Headache - Continue study medication with dose escalation as planned.

Somnolence or drowsiness - Continue study medication with dose escalation as planned. Inform patient that this symptom generally subsides after a few weeks. Patient can move the time for medication from 30 min before bedtime to 60 minutes before bedtime. If continues, reduce dose to prior tolerable dose and maintain this dose for remainder of study.

Tremor - This symptom generally subsides after a few weeks. If continues and intolerable for the patient, reduce dose to prior tolerable dose and maintain this dose for remainder of study.

Confusion - Stop medicine for one week, and then restart at lower tolerable dose.

**Cardiac:** Palpitations/Tachycardia: Obtain ECG and check QTc interval. If normal, stop medication for one week and resume at lower tolerable dose. If ECG is abnormal, instruct patient to stop taking the study drug, monitor and refer as appropriate.

**Ophthalmic:** Blurred vision - Continue study medication with dose escalation as planned. This symptom generally subsides after a few weeks. If continues and intolerable, reduce dose to prior tolerable dose and maintain this dose for remainder of study.

**Urinary:** Urinary Retention - Continue study medication with dose escalation as planned. This symptom generally subsides after a few weeks. If continues and intolerable, reduce dose to prior tolerable dose and maintain this dose for remainder of study.

**Dermatologic:** Skin rash - Investigate if there are other potential causes for skin rash. If tolerable by patient, continue medication with dose escalation as planned. If skin rash worsens during the study, reduce dose to prior tolerable dose and maintain this dose for remainder of study. If skin rash continues to worsen, stop the study medication. Patient remains in study on no treatment.

**Other:** Fatigue - Continue study medication with dose escalation as planned. Inform patient that this symptom generally subsides after a few weeks. Patient can move the time for medication from 30 min before bedtime to 60 minutes before bedtime. If continues, reduce dose to prior tolerable dose and maintain this dose for remainder of study.

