### 3.4 Restarts and dose adjustments due to side effects

A standardized management plan for potential side effects and symptoms is detailed in section 5.7 Safety issues. If a common, non-serious side effect to the study drug develops which is noticeable but tolerable, investigators will follow a standardized management plan as outlined in section 5.7 of the protocol. These side effects include ones commonly seen with TCAs such as constipation, dry mouth, weight gain, bloating, dizziness, insomnia. The management plan for these common, non-serious side effects generally involves patient education about the side effect and adding over the counter therapies. The study drug is continued with dose escalation. If the side effect becomes bothersome and barely tolerable, then the study drug dosage is reduced to the last dose tolerated without stopping treatment. If the side effect is intolerable, then the study drug is discontinued for one week and then restarted at the lower dosage that was previously tolerated.

If side effects occur that may be more serious, such as heart palpitations, skin rash, anxiety, confusional states, panic, then the patient will be evaluated. For heart palpitations, an ECG will be

obtained. Investigators can initially attempt dose reduction to the previous well tolerated dose instead of treatment interruption. If patients developed serious or intolerable side effects requiring cessation of study drug, the drug will be stopped for one week. If the side effects disappear, a second attempt will be made to reintroduce the study drug after one week at the previous lower dose that the participant tolerated better. If the dose is well tolerated, the patient will be continued at this dose for the remainder of the study without further dose escalation. If the study medication is stopped, the patient will no longer receive the study drug, but will be followed in the study according to the protocol, in keeping with the "intention-to treat" paradigm.

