#### **SERIOUS SIDE EFFECTS FOR WHICH STUDY MEDICATION WILL BE STOPPED AND THE PATIENT WILL BE FOLLOWED ON NO TREATMENT.**

Patients will call in if they develop blurred vision, rapid heart beat, chest pain, orthostatic hypotension, dizziness upon standing or difficulty urinating.

**Cardiovascular:** Cardiac dysrhythmias, QTc prolongation (concern is for >440 – 450 msec in men or > 460 – 470 msec in women), concern for development of Torsades de Pointes or sudden death heartblock on ECG myocardial infarction (rare). Stop study medication. Ensure immediate follow-up with a cardiologist. Patient remains in study on no treatment. Repeat ECG after stopping study medication.

**Hematologic:** Agranulocytosis (rare), bone marrow depression (rare), drug-induced eosinophilia (rare), thrombocytopenia (rare). Stop study medication. Ensure immediate follow-up with a hematologist. Patient remains in study on no treatment.

**Hepatic:** Decreased liver function (rare), jaundice (rare). Stop study medication. Ensure immediate follow-up with a hepatologist. Patient remains in study on no treatment.

**Dermatologic:** Signs of an allergic reaction – unexplained hives, unexplained swelling, wheezing, swelling of face, lips, tongue, or throat. Stop medicine. Instruct patient to call 911 or go to emergency room for immediate care. Patient remains in study on no treatment.

**Neurologic:** Cerebrovascular accident (rare), seizure (rare). Stop study medication. Ensure immediate follow-up with a neurologist. Patient remains in study on no treatment.

**Psychiatric:** Depression, worsening, suicidal thoughts, suicide - Stop medicine. Refer to mental health professionals. Patient remains in study on no treatment. Symptoms of aggressiveness, akathisia (psychomotor restlessness), agitation, anxiety, insomnia, irritability, hostility, mania, impulsivity, and panic attacks may represent precursors to emerging suicidality.

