## 6.2 Outcome measures

### Primary outcome measure:

The primary outcome measure is defined as a decrease from the baseline GCSI score (sum of the 9 individual symptom scores) of at least 50% on any two consecutive follow-up visits during the 15 week treatment period with maximum tolerated study drug dose. A sensitivity analysis will compare cumulative GCSI symptom scores averaged across all follow-up visits to rule out the possibility that an effect present in the primary analysis was due to the GCSI score decreasing 50% on two consecutive visits with smaller improvement or worsening on other follow-up visits.

All patients will be followed for the full 18 weeks after randomization regardless of response or

course of treatment to permit an intention-to-treat primary analysis.

The GCSI total score ranges from 0 to 45 (highest severity) and is calculated as the sum of nine individual symptom scores:

$$\begin{aligned} \text{GCSI} = & \text{Nausea (0-5) +} \\ & \text{Retching (0-5) +} \\ & \text{Vomiting (0-5) +} \\ & \text{Stomach fullness (0-5) +} \\ & \text{Not able to finish a normal sized meal (0-5) +} \\ & \text{Feeling excessively full after meals (0-5) +} \\ & \text{Loss of appetite (0-5) +} \\ & \text{Bloating (0-5) +} \\ & \text{Stomach visibly larger (0-5)} \end{aligned}$$

As noted earlier, a GCSI score of 21 or greater is a requirement for enrollment into the trial. The primary outcome measure is a binary (0, 1) variable, which equals to 1, if a GCSI score reduction of 50% or greater, relative to the baseline score, is observed on at least two consecutive follow-up visits during the 15 weeks of treatment and follow-up.

**Secondary outcome measures** will be defined to address the following areas:

- (1) Symptoms
  - Subscores for the GCSI such as nausea/vomiting, postprandial fullness, bloating
  - Individual symptom scores
  - Global overall relief of symptom questionnaire
  - Clinical global patient impression
- (2) Physiology
  - Satiety test: Volume of Ensure® consumed during satiety testing
  - Electrogastrography: Percent time in EGG dysrhythmias (outside 2.5-3.75 cycles per minute)
  - Side effects to treatment requiring stopping medication

**Subgroup differences** in response to nortriptyline will be addressed:

- (1) Differential response to nortriptyline based on pharmacogenetic analysis of patients
- (2) Differential response to nortriptyline based on blood levels of nortriptyline

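### Sections 3.4 and 5.7 give different dose actions for the same side effect: a one-week stop in one place, a dose reduction without a stop in another

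*Protocol*

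**What the plan says.** Sections 3.4 and 5.4 both refer to section 5.7 for managing side effects. Under common side effects, 5.7 gives a three-step severity table and then a list by symptom.

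- **Severity table (5.7).** Noticeable but tolerable: "Continue therapy and dose escalation". Barely tolerable: reduce to the last tolerated dose without stopping. Intolerable: "Discontinue nortriptyline for one week and then restart it at the lower dosage that was previously tolerated".
- **Section 3.4, common effects.** This matches the table: "If the side effect is intolerable, then the study drug is discontinued for one week and then restarted at the lower dosage".
- **Per-symptom list (5.7).** For blurred vision and urinary retention: "If continues and intolerable, reduce dose to prior tolerable dose and maintain this dose for remainder of study". The tremor entry has the same substance. For dizziness, somnolence and fatigue, the dose is reduced and held if the symptom continues, with no severity condition. Confusion calls for a one-week stop. For palpitations, after an ECG: "If normal, stop medication for one week and resume at lower tolerable dose".
- **Section 3.4, effects that may be more serious.** Palpitations and confusional states are named here: "Investigators can initially attempt dose reduction to the previous well tolerated dose instead of treatment interruption".
- **Section 5.4.** The investigator can reduce the dose or, for significant side effects, may stop therapy for one week, as outlined in 5.7.
- **Section 6.2.** The secondary outcomes include "Side effects to treatment requiring stopping medication".

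**The concern.** A clinic with a patient who has intolerable tremor, blurred vision or urinary retention cannot follow both the table and the list. One interrupts the drug and the other does not. Referring the reader to 5.7 does not help, because both texts are in 5.7 and neither is said to take precedence.

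Three things depend on the answer:

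- **Patient management.** These are safety instructions, and two clinics could treat the same patient differently while each complied with the Protocol.
- **Exposure.** The rules decide time off drug during the 15-week treatment period.
- **The stopping outcome.** The same event involves a discontinuation under one text and none under the other, so the count partly reflects which text each clinic used. Section 3.4 adds to this by using the same verb for a one-week pause and for permanent cessation.

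**Working it through.** **Step 1: set the texts side by side.**

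| Symptom and state | 3.4 | 5.7 table | 5.7 list |
|---|---|---|---|
| Tremor, blurred vision, urinary retention; intolerable | Stop one week, restart lower | Stop one week, restart lower | Reduce and hold, no stop |
| Palpitations with normal ECG; confusion | Reduction may be tried first in place of interruption | Graded by severity only | Stop one week, resume lower |
| Dizziness, somnolence, fatigue; persistent but tolerable | Escalation continues for tolerable common effects (dizziness is named) | Continue and escalate | Reduce and hold on persistence alone |

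- Row 1 (three symptoms) is a direct contradiction. The trigger is the same, intolerability, and the directed actions differ.
- Row 2 (two symptoms) sets a permission against a direction. An investigator who uses the option in 3.4 departs from the list.
- Row 3 (three symptoms) sets a severity trigger against a persistence trigger. A mild effect that lasts is escalated under one and reduced under the other.

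**Step 2: look for a rule of precedence.** Sections 3.4 and 5.4 point to 5.7. Section 5.7 introduces the table and the list together as one standardized plan and does not rank them.

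**Step 3: size the exposure difference for row 1.** Inputs are the 15-week treatment period and the one-week pause.

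- List: the patient moves to the lower dose at once and stays there.
- Table and 3.4: the patient takes nothing for one week and then the lower dose. The second paragraph of 3.4 holds that dose without further escalation after a serious or intolerable effect that required cessation.
- Difference: one week off drug instead of one week at the lower dose. 7 days / (15 × 7 = 105 days) = 1/15 = 6.7%.
- Difference in time at the top dose: none, because both routes leave the higher dose at the same moment and do not return to it.

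**Step 4: check the per-protocol set.** Section 6.3 requires at least 60% of treatment: 0.60 × 15 = 9 weeks, which agrees with the figure stated there. One pause leaves 14/15 = 93.3%, so it does not by itself exclude a patient.

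**Step 5: check the primary analysis.** Sections 6.2 and 6.3 follow all patients regardless of treatment course and analyse them as assigned. Assignment does not depend on which text was used.

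**The case against.** **What stands on the other side.** The conflict for palpitations and confusion is softer than that for intolerable effects, because 3.4 only permits reduction. Randomization is masked and stratified by clinic, and 6.3 tests binary secondary outcomes with clinic-stratified tables. Site habits therefore fall on both arms. They can change the size of a difference in stopping rates but would not create one. Whether a one-week pause counts as stopping may be defined in a statistical analysis plan that is not shown. Such a plan could settle the counting, but not which action the clinic should have taken.

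**Stronger readings that the Protocol does not support.**

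- A reader might infer from the heading of the serious-effects part of 5.7 that blurred vision, rapid heart beat or difficulty urinating require a permanent stop. The sentence orders only a call: "Patients will call in if they develop blurred vision, rapid heart beat, chest pain, orthostatic hypotension, dizziness upon standing or difficulty urinating". The explicit stop instructions belong to the categories that follow it.
- A reader might see insomnia as both a common effect with continued escalation and a reason to stop. In the psychiatric paragraph it is only a possible precursor, with no action attached.
- A reader might think that the plain continue entries, such as nausea, constipation and headache, override the table. They can be read as its tolerable step, with the table supplying the other two.
- A reader might count the pause as one of the six planned weeks at the top dose. Step 3 shows why that is wrong.
- A reader might want the number of patients reclassified. The Protocol gives no event rates, so any such number would be pure assumption.

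**Conclusion.** The Protocol is wrong as written on this point. For intolerable tremor, blurred vision and urinary retention, 5.7 directs two incompatible actions, and 3.4 sides with the table. The conflicts for palpitations with a normal ECG and confusion, and for persistent dizziness, somnolence and fatigue, are real but secondary.

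The effect is limited. Each affected patient differs by one week off drug, 6.7% of the treatment period, with no difference in time at the top dose. This assumes a single pause and that the no-further-escalation rule in 3.4 applies after the restart; the table itself is silent on re-escalation. The secondary stopping outcome is directly exposed. The primary intention-to-treat assignment is unaffected, and the per-protocol set is hardly touched. The reason to act is that these are safety instructions feeding a named outcome and the repair is cheap.

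**What to change.** The sponsor should reconcile 3.4, 5.4, the 5.7 severity table and the 5.7 symptom entries so that one text governs each symptom and severity. Which action applies is the sponsor's clinical decision. Investigator discretion may remain, provided that it is stated in that one place. Sections 3.4 and 5.4 should then refer to that text and not restate the rules.

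For the stopping outcome in 6.2, report temporary interruption and permanent stop separately.

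As a tidy-up only, separate the call-in sentence from the heading that says medication will be stopped.

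The cost is Protocol wording, with no added visits, procedures or patients.

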#### **SERIOUS SIDE EFFECTS FOR WHICH STUDY MEDICATION WILL BE STOPPED AND THE PATIENT WILL BE FOLLOWED ON NO TREATMENT.**

Patients will call in if they develop blurred vision, rapid heart beat, chest pain, orthostatic hypotension, dizziness upon standing or difficulty urinating.

**Cardiovascular:** Cardiac dysrhythmias, QTc prolongation (concern is for >440 – 450 msec in men or > 460 – 470 msec in women), concern for development of Torsades de Pointes or sudden death heartblock on ECG myocardial infarction (rare). Stop study medication. Ensure immediate follow-up with a cardiologist. Patient remains in study on no treatment. Repeat ECG after stopping study medication.

**Hematologic:** Agranulocytosis (rare), bone marrow depression (rare), drug-induced eosinophilia (rare), thrombocytopenia (rare). Stop study medication. Ensure immediate follow-up with a hematologist. Patient remains in study on no treatment.

**Hepatic:** Decreased liver function (rare), jaundice (rare). Stop study medication. Ensure immediate follow-up with a hepatologist. Patient remains in study on no treatment.

**Dermatologic:** Signs of an allergic reaction – unexplained hives, unexplained swelling, wheezing, swelling of face, lips, tongue, or throat. Stop medicine. Instruct patient to call 911 or go to emergency room for immediate care. Patient remains in study on no treatment.

**Neurologic:** Cerebrovascular accident (rare), seizure (rare). Stop study medication. Ensure immediate follow-up with a neurologist. Patient remains in study on no treatment.

**Psychiatric:** Depression, worsening, suicidal thoughts, suicide - Stop medicine. Refer to mental health professionals. Patient remains in study on no treatment. Symptoms of aggressiveness, akathisia (psychomotor restlessness), agitation, anxiety, insomnia, irritability, hostility, mania, impulsivity, and panic attacks may represent precursors to emerging suicidality.

Treatment with antidepressant agents have been reported to paradoxically be associated with suicide in patients with primary depression. Primary depression is an exclusion for participation in the NORIG trial. We will monitor patients for the most common severe serious side effects (cardiac and psychiatric) by using standardized questionnaires for side effects and the Beck Depression Inventory (BDI) score. The Suicidal Thoughts or Wishes item in statement 9 on the BDI-II will be used to determine if a patient is suicidal. A score of 1 on this item (I have thoughts of killing myself, but would not carry them out) should initiate a referral to a mental health professional for further investigation. A score of 2 (I would like to kill myself) or 3 (I would kill myself if I had the chance) should result in contacting the mental health consultant (pager/phone) for discussion about disposition, i.e., immediate meeting with the mental health consultant or getting the patient to the ER for possible inpatient treatment.

Also, severe depression is suggested by a patient response of 2 or 3 in the BDI-II statement 2 on Pessimism or a score of 28 or more total points on the BDI. With either a response of 2 or 3 on statement 2 or a total score of 28 or more, and in the absence of the suicide item trigger, this would result in a referral to the mental health consultant. Study staff will calculate the BDI total score and check statements 2 and 9 before the patient leaves. For each clinical center, a mental health professional (psychiatrist or psychologist) will be part of the study. Each consent form given to participants will have a self-referral list for psychological assistance if needed. In sum,

- If Severe Depression (BDI-II total > 28) with Statement 9 = 1; then refer for further mental health evaluation as soon as can be arranged (usually same day if patient is agreeable)
- If Suicidal Ideation without intent on Statement 9 = 1; then refer for further mental health evaluation as soon as can be arranged (usually same day if patient is agreeable)
- If Suicidal Ideation with possible intent on Statement 9 > 1; then contact mental health consultant immediately for further evaluation and disposition; handle as possible psychiatric emergency

Approximately half of the patients in NORIG will be assigned to the placebo group and will receive matching placebo instead of nortriptyline for the length of the study. The risks of receiving placebo are the same as not receiving any additional treatment for gastroparesis symptoms. All NORIG participants will be allowed to take the rescue medications for nausea, vomiting, and abdominal pain.

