#### 4.3 Exclusion criteria

Patients who satisfy any of the following exclusion criteria will be ineligible for randomization in the trial:

1. Normal gastric emptying confirmed with scintigraphy
2. Diabetic gastroparesis or post-surgical gastroparesis including fundoplication
3. Another active disorder which could explain symptoms in the opinion of the investigator
4. History of significant cardiac arrhythmias and/or prolonged QTc
5. History of seizures
6. Use of narcotics (including fentanyl patches) more than 3 days per week
7. Use of tricyclic antidepressants for refractory symptoms of gastroparesis within 6 weeks prior to randomization
8. Use of strongly anticholinergic medications
9. Use of calcium channel blockers
10. Use of erythromycin
11. Clear history of failed trial of nortriptyline use for gastroparetic symptoms
12. Symptoms of primary depression or suicidal ideation
13. Contraindications to nortriptyline:
  - a) hypersensitivity or allergy to any tricyclic antidepressant
  - b) concomitant therapy with a monoamine oxidase inhibitor (MAOI)
  - c) recent myocardial infarction
  - d) glaucoma
14. Pregnancy or nursing
15. Any other condition, which in the opinion of the investigator would impede compliance or hinder the completion of the study
16. Use of a G tube, J tube, or a central catheter for nutrition
17. Use of a gastric electrical stimulator
18. Failure to give informed consent

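### The closing summary list in Protocol section 5.7 has no referral for severe depression with BDI-II Statement 9 = 0, although the narrative above it requires one

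*Protocol*

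**What the plan says.** The psychiatric monitoring text in Protocol section 5.7 first sets out the rule in prose. A Statement 9 score of 1 starts a referral to a mental health professional, and a score of 2 or 3 means contacting the mental health consultant. The text then turns to depression itself: "severe depression is suggested by a patient response of 2 or 3 in the BDI-II statement 2 on Pessimism", or by a total of 28 or more. For either sign the narrative says: "a total score of 28 or more, and in the absence of the suicide item trigger, this would result in a referral" to the consultant. Staff are also told: "Study staff will calculate the BDI total score and check statements 2 and 9 before the patient leaves".

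A three-bullet list then presents itself as the summary of this rule:

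- Bullet 1: "If Severe Depression (BDI-II total > 28) with Statement 9 = 1; then refer for further mental health evaluation".
- Bullet 2: "If Suicidal Ideation without intent on Statement 9 = 1; then refer for further mental health evaluation".
- Bullet 3: Statement 9 above 1 leads to immediate contact with the consultant.

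Bullets 1 and 2 carry the same timing clause (as soon as possible, usually the same day).

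**The concern.** The list does not restate the rule above it. A Statement 9 score of 1 is itself a trigger, so the narrative's depression rule, which applies when that item is not triggered, concerns Statement 9 = 0. Bullet 1 attaches severe depression to Statement 9 = 1. Every bullet therefore needs Statement 9 of at least 1, and a severely depressed patient who reports no suicidal thoughts has no line in the list.

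This is a patient-safety decision rule in a trial of an antidepressant, and the protocol names the BDI-II as one of its safety monitors. Staff must score the form before the patient goes home, and a short closing list is what they are likely to work from. If they use it alone, they can miss a referral that the narrative requires. Under section 9.2 the BDI-II is given at six visits after randomization (weeks 3, 6, 9, 12, 15 and 18), so the question can arise six times per patient. The screening administration comes before study drug.

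**Working it through.** The plan states no figure to reproduce. The check compares two versions of a decision rule.

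**The two versions**

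| Statement 9 | Narrative | List |
|---|---|---|
| 2 or 3 | contact the consultant | contact the consultant immediately (bullet 3) |
| 1 | refer | refer (bullet 2; bullet 1 repeats it for totals above 28) |
| 0 | refer if total ≥ 28 or Statement 2 is 2 or 3; otherwise no action | nothing stated |

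**Bullet 1 against the narrative.** Three elements differ:

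- Statement 9 = 1 instead of 0;
- total > 28 instead of ≥ 28;
- no Statement 2 criterion.

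**Grouped patterns.** Take the total as below 28, exactly 28 or above 28; Statement 2 as 0–1 or 2–3; and Statement 9 as 0, 1, 2 or 3. This gives 3 × 2 × 4 = 24 patterns. All disagreements have Statement 9 = 0:

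- total below 28 with Statement 2 = 2–3: 1 pattern
- total exactly 28, either Statement 2 group: 2 patterns
- total above 28, either Statement 2 group: 2 patterns

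The sum is 5. Changing only the Statement 9 digit to 0 leaves 3. Changing > 28 to ≥ 28 as well leaves 1. Restoring Statement 2 as well leaves 0. Giving a total of exactly 28 its own group does not create the result: with totals split only at 28 (16 patterns), the same steps give 3, 1, 1 and 0.

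**Every integer score.** Section 5.5 gives 21 items. Assume that each is scored 0–3. For each pair (Statement 2 = a, Statement 9 = b), the other 19 items add 0 to 57, so the total runs from a + b to a + b + 57, which is 58 values. There are 16 × 58 = 928 feasible patterns. The disagreements, all at Statement 9 = 0, are:

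| Version of bullet 1 | Statement 2 = 0 | 1 | 2 | 3 | Sum |
|---|---|---|---|---|---|
| As written | 30 | 31 | 58 | 58 | 177 |
| Statement 9 changed to 0 | 1 | 1 | 27 | 26 | 55 |
| and threshold ≥ 28 | 0 | 0 | 26 | 25 | 51 |
| and Statement 2 restored | 0 | 0 | 0 | 0 | 0 |

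The 177 split into 126 with a total of 28 or more and 51 with a lower total but Statement 2 = 2 or 3.

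**What bullet 1 adds.** It applies to 126 patterns (total above 28, Statement 9 = 1). Bullet 2 already refers all 126 with the same action and timing, so bullet 1 adds 0.

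**The case against.** The strongest reply is that the list is incomplete and does not contradict the narrative. It never says that Statement 9 = 0 needs no referral, and nothing makes it override the prose. Staff who read all of the text make every required referral. The instruction to check Statement 2 has no purpose under the list alone, so it sends the reader back to the narrative.

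There are other safeguards. The serious side effects text says: "Depression, worsening, suicidal thoughts, suicide - Stop medicine. Refer to mental health professionals". Section 4.3 excludes "Symptoms of primary depression or suicidal ideation". Each center has a mental health professional.

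Much of this stands and limits the risk, but it does not remove the defect. The list claims to sum up the rule, one of its thresholds plainly conflicts with the narrative, and its severe-depression bullet adds no patient. The general psychiatric instruction has no score cut-off. The exclusion acts at entry, not on depression that emerges during treatment.

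Two smaller points are fair. Score-pattern counts say nothing about how often the gap would be met. For Statement 9 of 1 or more, both texts send the same patients to the same kind of help, but the list adds wording on urgency that the narrative lacks.

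**Conclusion.** The concern holds, as an internal inconsistency in a safety rule that should be fixed. The narrative is complete; its summary is wrong in three respects and errs only toward missed referrals. The gap is confined to Statement 9 = 0.

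The conclusion rests on the wording alone. Only the 928-pattern count needs the assumption of 0–3 item scoring. The protocol gives no BDI-II score distribution, so the number of patients affected cannot be estimated. That bullet 1 was meant to say Statement 9 = 0 is an inference, but it is the only value that matches the narrative. Sample size, error rates and the primary analysis are not affected.

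**What to change.** Replace bullet 1 with a bullet to this effect: severe depression (BDI-II total ≥ 28, or Statement 2 = 2 or 3) with Statement 9 = 0 leads to referral to the mental health consultant, with the timing clause that bullet 1 now carries. Leave bullets 2 and 3 as they are. All three elements need repair, since correcting the Statement 9 digit alone still leaves a total of exactly 28 and the Statement 2 route uncovered.

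The narrative sets no timing for this referral. Keeping the clause preserves the flexible timing already attached to severe depression in the list. If the sponsor prefers not to set a timing, the clause can be left out without changing who is referred.

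The cost is one replaced bullet, with no added visits, procedures or patients.
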